Official Title of Study: CPAP to Improve Swallow Function Post Total Laryngectomy

NCT# 03328702

Document Date May 20, 2016

Attached is the UC Davis IRB approved Protocol and there have been no protocol changes since 2016.

Sincerely,

A handwritten signature in black ink, appearing to read "[name]".

[name]., M.P.H., Ph.D.

Department of Otolaryngology Head and Neck Surgery

University of California, Davis School of Medicine

PROTOCOL TITLE: Utilization of Continuous Positive Airway Pressure to Improve Swallow Function in Patients Post Total Laryngectomy

1) Protocol Title

Utilization of Continuous Positive Airway Pressure to Improve Swallow Function in Patients Post Total Laryngectomy

Version date: 5.3.16

2) Objectives

To determine whether use of Continuous Positive Airway Pressure (CPAP) can improve the swallow function in patients who underwent total laryngectomy and are experiencing difficulty swallowing.

3) Background

Total laryngectomy is a procedure that involves surgical removal of the larynx and separation of the digestive and airway tracts. The procedure is typically conducted for cases of laryngeal cancer and intractable aspiration. Following this procedure, patients are no longer at risk for aspiration; however some patients continue to experience difficulties in propulsion of food or drink throughout the pharynx. These difficulties can result from pharyngeal neuromuscular damage caused by surgery and radiation (1). Previous research has demonstrated a reduction in pharyngeal contractile pressure and increased pharyngeal transit time in patients post laryngectomy (2,3). Continuous Positive Airway Pressure (CPAP) may assist bolus propulsion in these patients by increasing pressure in the direction of bolus flow. This study aims to evaluate the utility of a CPAP mask to improve pharyngeal swallow outcomes in patients with dysphagia following total laryngectomy. This specific population could be well-suited for this application, since the digestive tract and airway are completely separate and there is no risk of the aspiration into the airway.

PROTOCOL TITLE: Utilization of Continuous Positive Airway Pressure to Improve Swallow Function in Patients Post Total Laryngectomy

4) Inclusion and Exclusion Criteria

Inclusion criteria:

- Age \geq 18 years.
- Patients at least 2 months after total laryngectomy undergoing a dynamic swallow study (DSS).

Exclusion criteria:

- Patients with 100% neopharyngeal stenosis

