- Patients with active cancer within 2 months of the study
- Patients with pharyngocutaneous fistula
- Vulnerable population:
 - Adults unable to consent
 - Individuals who are not yet adults (infants, children, teenagers)
 - Pregnant women
 - Prisoners

5) Study Timelines

The subjects will be in study from the time they sign the consent form to completion of the videofluoroscopy study. Approximately 5 additional minutes will be added to each subject's clinical DSS study, with no more than 1-2 seconds of additional fluoroscopic exposure. The estimated date of complete of the study will be 12 months after IRB approval.

6) Study Endpoints

Primary endpoint of the study is complete videofluoroscopic data for all 10 patients.

7) Procedures Involved

Each subject will undergo a standard DSS for the purpose of medical diagnosis. The research study portion will be incorporated into the procedure for patients who consent to participation in the study. The dynamic swallow study is a radiologic examination of swallowing function using fluoroscopy. Standard examinations consist of multiple radio-opaque boluses of different consistencies. During a standard videofluoroscopic study, subject are asked to

PROTOCOL TITLE: Utilization of Continuous Positive Airway Pressure to Improve Swallow Function in Patients Post Total Laryngectomy

swallow barium-coated foods of the following volumes and consistencies in side and front view. Swallows can be added to the protocol in order to assess clinical questions relevant to each specific patient.

Lateral Plane

- 1 ml liquid barium (X2)
- 20 ml liquid barium (X2)
- 60 ml thin liquid barium consecutive sips via straw
- 3 ml pudding

Anterior-to-Posterior Plane

- 20 ml liquid barium
- 13 mm barium tablet

In order to minimize exposing participants to additional radiation during this study, the patients will be asked to wear the CPAP mask during standard swallows test for one of the two swallows of the following consistencies in side view:

- 1 ml thin liquid barium
- 20 ml thin liquid barium

One additional 3ml pudding bolus swallow with the CPAP mask will be added in order to compare swallow function of a pudding consistency with and without the CPAP. This additional swallow will add no more than 1-2 seconds of videofluoroscopic exposure time.

8) Data and/or Specimen Management and Confidentiality

The measures explained in the online application will be taken to protect the confidentiality of subjects:

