Videofluoroscopic data collected from the above protocol will be analyzed by paired sample T test and repeated measures of analysis of variance. Data will be stored anonymously and securely, accessible with a password available only to participating researchers.

9) Data and/or Specimen Banking

N/A

PROTOCOL TITLE: Utilization of Continuous Positive Airway Pressure to Improve Swallow Function in Patients Post Total Laryngectomy

10) Provisions to Monitor the Data to Ensure the Safety of Subjects

N/A. This study does not pose more than a minimal risk to subjects.

11) Withdrawal of Subjects

Subjects unable to complete the entire protocol may be withdrawn from the study and not included in data analysis.

12) Risks to Subjects

Patients are undergoing the videofluoroscopic procedure as standard of care. One additional swallow will be added to the standard protocol, adding a minimal 1-2 seconds of fluoroscopic exposure time.

The risks of the CPAP device include skin irritation, dry mouth, nasal congestion. These risks are unlikely to occur during this study in which patients will be wearing the mask for only several minutes. Subjects may experience stomach bloating. Subjects may experience discomfort from wearing the mask.

13) Potential Benefits to Subjects

No direct benefit to participating subjects is anticipated.

14) Multi-Site Research

N/A

15) Sharing of Results with Subjects

Results will not be shared with subjects.

16) Prior Approvals

Radiation Use Committee approval was obtained before IRB submission

17) Provisions to Protect the Privacy Interests of Subjects

Subjects will undergo the protocol privately with a limited number of qualified personnel present. Beyond determining eligibility as described above, no personal or medical information will be sought from participants. The procedure will be limited to only what is described in the above protocol. Only qualified research personnel working on the project will access subjects' secure data, which will be password-protected.

PROTOCOL TITLE: Utilization of Continuous Positive Airway Pressure to Improve Swallow Function in Patients Post Total Laryngectomy

18) Compensation for Research-Related Injury

N/A. The study procedure does not pose more than minimal risk to subjects.

19) Economic Burden to Subjects

N/A

20) Drugs or Devices

N/A

References

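### The plan has no systematic record of bloating, mask discomfort or reasons for non-completion, although Section 12 names both effects and Section 17 limits what may be asked

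*Combined protocol and SAP*

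**What the plan says.** **Risks (Section 12).** Three CPAP risks come first: "The risks of the CPAP device include skin irritation, dry mouth, nasal congestion". The next sentence calls these unlikely because the mask is worn only for several minutes. Two further effects follow without that reassurance: "Subjects may experience stomach bloating. Subjects may experience discomfort from wearing the mask". No rate is given for any of the five.

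**Information sought (Section 17).** The privacy section says "Beyond determining eligibility as described above, no personal or medical information will be sought from participants", and adds: "The procedure will be limited to only what is described in the above protocol". Section 7, which sets out the procedure, contains swallows only and no symptom or tolerability question.

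**Non-completion (Section 11).** A subject who cannot finish the whole protocol may be withdrawn and omitted from the analysis. The section does not say whether the reason, or the number of such subjects, is recorded or reported.

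**Other places where such a record might appear.** Section 10 (safety monitoring) is marked not applicable on grounds of minimal risk. Section 6 makes complete videofluoroscopic data on all 10 patients the primary endpoint. Section 8 names only videofluoroscopic data for analysis. Section 5 closes the observation period with the film: "The subjects will be in study from the time they sign the consent form to completion of the videofluoroscopy study".

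**The concern.** Bloating and mask discomfort are mainly felt by the subject, and a swallow film is not designed to show them. Capturing them in every subject means asking, and a site that follows Section 17 literally would not ask.

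Section 11 adds to the gap. If someone stops because of the mask, the plan permits that person to be dropped, and no reason need be kept. The reported results could then describe only those who tolerated CPAP, without saying so. A reader of the final report could not tell whether an absence of reported discomfort meant that nobody had any or that nobody was asked.

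**Working it through.** The plan gives no figure on this point, so there is none to reproduce. The check is first a comparison of sections, then a short calculation of what 10 answers would be worth.

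**Step 1: is there any route by which the two effects are recorded?**

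| Section | What it provides | Captures bloating or discomfort? |
|---|---|---|
| 5 | Participation ends with the film | No later contact |
| 6 | Endpoint: complete film data, 10 patients | No |
| 7 | Swallows with and without the mask | No question described |
| 8 | Analysis of videofluoroscopic data | No |
| 10 | Safety monitoring: not applicable | No |
| 11 | Non-completers may be withdrawn and excluded | Reason not mentioned |
| 12 | Names both effects as possible | Names them, does not measure them |
| 17 | Nothing medical sought beyond eligibility; procedure limited to what is described | Read literally, excludes asking |

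The number of planned tolerability variables is zero.

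**Step 2: what would asking all 10 subjects give?** The input is n = 10 (Section 6). Event rates are assumptions, since the documents give none.

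- Zero events, one-sided 95% upper limit: 1 − 0.05^(1/n). For n = 10, 1 − 0.05^(1/10) = 0.259, or 26%.
- Three events in 10, exact (Clopper-Pearson) two-sided 95% interval: 6.7% to 65.2%.
- Chance of at least one report at true rate p: 1 − (1 − p)^10.

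| Assumed rate p | Chance of at least one report in 10 |
|---|---|
| 5% | 1 − 0.95^10 = 40% |
| 10% | 1 − 0.90^10 = 65% |
| 20% | 1 − 0.80^10 = 89% |
| 30% | 1 − 0.70^10 = 97% |

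Ten answers would probably reveal a common problem. They could not exclude an uncommon one.

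**Step 3: what does dropping non-completers do?** Each subject is 1/10 = 10% of the sample. Suppose, purely as an illustration, that 2 of the 10 stop because of mask discomfort and are excluded, and that the other 8 have none. The retained data then show 0 of 8, with upper limit 1 − 0.05^(1/8) = 0.312, or 31%. The full count is 2 of 10 = 20%. The larger error is the lost numerator: two intolerant subjects become none.

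**The case against.** The strongest reply is that Section 17 is a privacy clause. It limits what is sought and does not forbid staff to note a volunteered complaint or a mask taken off. That stands. A reader might infer an outright ban on recording harms, but the wording supports only the absence of a planned, systematic record.

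A reader might also take the stated aim to be net benefit, so that it fails without harm data. The Background sentence does not say this: "This study aims to evaluate the utility of a CPAP mask to improve pharyngeal swallow outcomes". Section 2 likewise asks only whether swallowing can improve. The film addresses that question without symptom data.

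A third tempting inference is that air driven along with the bolus makes bloating the effect most likely to cancel any gain. The documents give no mechanism, rate or ranking for bloating, so the point does not rest on this.

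Nor is the contrast one of benefit measured against harm ignored. No specific film measure of swallow function is named either, and worse swallowing with the mask could appear on film.

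On Section 11, exclusion is permitted and not required. With an endpoint of complete data on all 10, a dropout might show as a shortfall. Replacement is not addressed, however, so a shortfall is not assured, and it would not reveal the reason.

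Finally, exposure is three mask swallows over several minutes, the study is described as minimal risk, and 10 answers give wide intervals. All of that is true. It limits the weight of the point and what the answers would say about longer use. It does not explain why effects the protocol itself names go unrecorded.

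**Conclusion.** The point holds as a reporting gap of modest size. Followed as written, Sections 11, 12 and 17 together leave no planned, systematic record of the two CPAP effects that Section 12 singles out, and a subject who cannot tolerate the mask may leave no trace in the results.

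The comparison of film measures with and without the mask is not invalidated among those who complete. What is lost is any count of how many tolerated the device. The conclusion assumes that sites apply Section 17 literally and that no case report form outside these documents already collects the items.

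The counts would be imprecise. They would also describe symptoms reported after the CPAP swallows, without proving that CPAP caused them. They should be presented descriptively, not as a test of safety.

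**What to change.** **Section 17.** Add an exception for a short tolerability record, taken after the last CPAP swallow or at early stopping, with three items: bloating (yes/no), mask discomfort (yes/no), and the reason for any non-completion. State that this record is part of the described procedure, so that it does not conflict with the section's own limit.

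**Section 11.** Require the number of non-completers and their reasons to be reported beside the film result, whether or not their films are analysed.

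**Reporting.** Give each count over all subjects in whom CPAP was attempted, with an exact binomial interval.

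A question on whether swallowing felt easier with the mask should not be added. It would be a new, unmasked efficacy outcome and is not needed here.

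**Cost.** Wording in two sections, a few more stored items per subject, and about one minute each. The minute is an assumption: Section 5 allows roughly 5 additional minutes but does not say how they are used. No extra swallow, radiation, staff or subjects are needed.
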